## XV. INDEPENDENT RADIOLOGICAL ASSESSMENT

### A. Quantitative Measurements

Quantitative measurements (angular and translational motion) will be produced by trained analysts using Quantitative Motion Analysis software (QMA®, Medical Metrics, Inc.). The software is US FDA 510(k) cleared and has been validated to produce assessments of intervertebral motion accurate to less than 1 degree and 1 mm (Zhao et al, *J Biomech* 2005; Reitman et al, *Spine* 2004). The reproducibility of the measurements has also been validated (Pearson et al, *Spine* 2011).

The measurements will be produced from flexion-extension views at the treated segments 6, 12 and 24 (as applicable) months postoperatively:

- Angular Motion (in units of degrees): Rotation of the superior vertebra relative to the inferior vertebra. Angular Motion will be measured in the sagittal plane from flexion-extension films.
- Translational Motion (in units of mm): Displacement of the posterior-inferior corner of the superior vertebra in a direction defined parallel to the superior endplate of the inferior vertebra. Translational Motion will be measured in the sagittal plane from lateral flexion-extension films.

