## 1. LAT, FLX & EXT X-Ray Guidelines

The x-ray system should be set up according to standard protocol for lateral lumbar spine x-ray.

- Include the calibration marker around the subject's waist and in the field of view in all lateral x-rays.

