## XIX. STATISTICAL METHODS

### ***A. Primary Endpoint***

The primary endpoint includes successful fusion of the treated segment(s) 12 months postoperatively based on the quantitative and qualitative assessments of the x-rays and CT scan. Fusion is defined as:

1. Presence of bridging trabecular bone [i.e. presence of left posterolateral bridging AND/OR right posterolateral bridging], **AND**
2. Angular motion < 5°, **AND**
3. Translational motion < 3 mm

The sample size and percentage of treated segments successfully fused will be presented. Sample sizes and percentages of treated segments successfully fused will be presented for different groups based on smoking status, age, sex, BMI, the number of segments treated and whether or not an IBF device was used.

Non-fusion will be defined as the failure to meet any one of the above criteria for fusion.

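### Segment motion is scored with no check that the participant bent, so a low-effort film pair passes both motion criteria; bridging must still be read, so the bias towards fusion is probably modest

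*Combined protocol and SAP*

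**What the plan says.** Section XIX.A defines fusion by three criteria that must all be met: "Presence of bridging trabecular bone [i.e. presence of left posterolateral bridging AND/OR right posterolateral bridging"; "Angular motion < 5" degrees; and "Translational motion < 3 mm". It adds: "Non-fusion will be defined as the failure to meet any one of the above criteria for fusion". A segment is therefore fused or not fused. There is no category for a film pair that cannot be assessed.

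On where motion is measured, section XV.A says: "The measurements will be produced from flexion-extension views at the treated segments 6, 12 and 24 (as applicable) months postoperatively". It describes the software as "accurate to less than 1 degree and 1 mm". That statement concerns reading the films, not the bending behind them.

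On how the films are taken, section XIII.D.1 says: "The x-ray system should be set up according to standard protocol for lateral lumbar spine x-ray". Its only other instruction is: "Include the calibration marker around the subject's waist and in the field of view in all lateral x-rays". Section XIII.E adds a scale and a side label. Neither section mentions how far the participant should bend, a minimum excursion or a reference level. The CT guidelines in XIII.D.3 point to a separate radiograph acquisition protocol, which is not among the supplied documents.

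Imaging differs by visit. X-rays are taken at 6, 12 and 24 months. CT is routine only at 12 months; at 24 months it depends on clinical indication, and an asymptomatic participant may decline it (XVI.G.3).

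**The concern.** An upper limit on motion between a flexion film and an extension film is informative only if the spine was bent between the two. A participant who hardly bends shows little motion at every level, and the treated segment then meets both limits whatever its state. The untreated lumbar levels on the same films could show this, but the plan does not measure them.

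The error has one direction. Too little bending can turn a motion failure into a pass, but not a pass into a failure. Within the fusion definition, the motion limits are the only check on a bridging grade that is wrong. That grade is fairly easy to obtain: one side suffices, bridging between facet joints counts, and a single reader decides (XV.B, XIX.A). The investigator's Lenke grade and the hardware assessment are recorded but are not part of the definition. At stake is the 12-month percentage of fused segments, together with the 6- and 24-month percentages, where bridging may be read without CT.

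**Working it through.** The plan gives no sample size calculation, alpha or power, and its primary result is a descriptive percentage. There is no figure of its own to reproduce. Two short calculations show how the mechanism works and how large it might be.

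**1. How much missing effort turns a failure into a pass**

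Inputs: the limits of 5° and 3 mm (XIX.A). Assumption: segment motion scales with the fraction of full effort.

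Formula: a limit is passed when effort is below limit ÷ full-effort motion.

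| Full-effort angular motion | Passes < 5° when effort is below |
|---|---|
| 6° | 5/6 = 83% |
| 8° | 5/8 = 62.5% |
| 10° | 5/10 = 50% |
| 12° | 5/12 = 42% |

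| Full-effort translation | Passes < 3 mm when effort is below |
|---|---|
| 3.5 mm | 3/3.5 = 86% |
| 4 mm | 3/4 = 75% |
| 5 mm | 3/5 = 60% |
| 6 mm | 3/6 = 50% |

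For a segment only slightly above a limit, a modest shortfall in bending is enough.

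**2. How much this could add to the fused percentage**

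A segment is wrongly credited through low effort only if four things coincide. The added share is

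(1 − F) × b × m × q

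- F: share of segments truly fused
- b: chance that bridging is read in a segment that is not fused
- m: chance that such a segment would exceed a motion limit at full effort
- q: chance that its film pair is low-effort enough to pass both limits

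All four are assumptions; the documents give none of them.

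- Smallest corner (F = 0.9, b = 0.1, m = 0.3, q = 0.1): 0.1 × 0.1 × 0.3 × 0.1 = 0.0003, or 0.03 points.
- Worked case (F = 0.8, b = 0.3, m = 0.6, q = 0.2): 0.2 × 0.3 × 0.6 × 0.2 = 0.0072, or 0.7 points. Without low effort the observed rate is 0.8 + 0.2 × 0.3 × 0.4 = 82.4%; with it, 83.1%.
- Largest corner (F = 0.7, b = 0.5, m = 0.6, q = 0.3): 0.3 × 0.5 × 0.6 × 0.3 = 0.027, or 2.7 points.

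For scale, take one segment per participant and 80% fused. The 95% half-width is 1.96 × √(0.8 × 0.2 / n): 11.1 points with n = 50 (the estimated enrolment, XII.C) and 10.1 points with n = 60 (the maximum, XII.B).

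**The case against.** The strongest reply is that low effort cannot produce a fusion by itself. An independent radiologist must also read bridging, with thin-slice CT at the primary time point. That stands, and it is why the estimate is small.

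A second reply is that every participant has bilateral instrumentation, and section XIII.C intends the fixation to be rigid. Where hardware already holds motion under the limits at full effort, an effort check changes nothing. This also stands: the check repairs only part of the motion criterion.

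Third, the radiograph acquisition protocol that was not supplied may contain bending instructions. It may. Even so, the scoring rule in XIX.A would still have no way to set aside a pair on which the instruction was not followed.

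Fourth, the films are kept and adequacy could be examined later. That is true, but a minimum chosen after the fusion results are known would carry less weight.

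Some stronger readings are tempting and are not supported:

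- A reader might infer a bias of 5 to 10 points by supposing that 3 to 6 of 60 segments are miscredited. That count is arbitrary. If 80% are truly fused, 12 of 60 are not, so it would require 25% to 50% of all non-unions to be miscredited in this way.
- A reader might infer that the comparison with the literature is tilted in the product's favour. The documents do not say whether the published studies checked effort.
- A reader might infer that painful participants both bend less and fail to fuse. Section XVII.A lists continuing pain and non-union as common complications, but nothing in the documents links either to effort on the films.

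**Conclusion.** The point holds in a limited form. Motion is measured only at the treated segments, the supplied documents contain no check that the participant bent, and a low-effort pair passes both motion criteria. The resulting error runs towards fusion and weakens the check on a false bridging reading, most of all at 6 months and at 24 months without CT.

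Its size is probably modest: about 0.03 to 2.7 percentage points over the assumed ranges, well inside the sampling uncertainty of roughly 10 to 11 points. The range rests on assumed values and on motion scaling with effort, and cannot be derived from the documents. A confidence interval would not reveal a bias of this kind. The change is worth making because it is cheap, not because the primary result is invalid without it.

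**What to change.** **Section XV.A, add:** on the same flexion and extension films, the same analysts will measure the total angular motion of the untreated, not previously fused lumbar segments in view.

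The restriction to levels not previously fused is needed because exclusion criterion 2 (XII.E) bars earlier fusion only at the segments to be treated.

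**Section XIX.A, add:** the fusion percentage as scored remains the primary result. A sensitivity analysis will report the number of treated segments whose film pair falls below an adequacy minimum, and the fusion percentage (a) with those segments counted as not fused and (b) with them excluded. The sponsor and the imaging laboratory will fix the minimum before the first 12-month film is read. If no unfused untreated segment is in view, adequacy is reported as unknown.

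The measurement covers all three visits, so the same count and percentages can accompany the 6- and 24-month results in XIX.B.

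The minimum should not be 5° pooled over all untreated segments. In the plan 5° is a limit for one segment. Spread over the four lumbar segments left by a one-segment fusion it is 5/4 = 1.25° each, close to the stated measurement accuracy. If the untreated segments total 30° at full effort (an assumption), it would trigger only below 5/30 = 17% effort, so it would catch only near-motionless pairs.

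**Cost:** some extra measurement work on films already transmitted, with no new imaging or reader. The fusion percentage may be slightly lower in the sensitivity analysis.

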### B. Qualitative Measurements

Qualitative assessments shall be performed by a single, independent radiographic reviewer that is board-certified, fellowship-trained, practicing neuro- or musculoskeletal radiologist. The following qualitative assessments shall be performed by a single, independent radiographic reviewer. The reviewer shall be a board-certified, fellowship-trained, practicing neuro- or musculoskeletal radiologist.

The qualitative assessments shall be conducted at the treated segments 6, 12 and 24 (as applicable) months postoperatively:

- Left & Right Posterolateral Bridging: X-rays as well as axial, coronal and sagittal CT reconstructions, when available, will be used to determine the presence of bridging. Assessment of bridging bone across the left and right posterolateral gutter, facet joint and/or transverse processes. Each treated segment will be graded separately. Posterolateral Bridging will be graded for each side (left and right) separately, and will include the entire posterolateral gutter, from the lateral-most aspect of the transverse processes to the medial-most aspects of the facet joints. Bridging between facet joints, between transverse processes, or between facet joint and transverse process will all be considered acceptable forms of bridging.
- Interbody Bridging: X-rays as well as axial, coronal and sagittal CT reconstructions,

when available, will be used to determine the presence of bridging. Assessment of bridging bone between the involved vertebral endplates. Each treated segment will be graded separately.

- Heterotopic Ossification
- Heterotopic bone formation will be evaluated to detect bone formation in unintended locations associated with the treatment.
- Hardware Condition: Assessment of device disassembly, loosening or fracture.
- Additional Observations: Other noteworthy observations will be documented at the radiologist's discretion.

## XVI. STUDY VISITS AND PROCEDURES

### A. Screening

The use of screening tests to assess whether prospective participants are appropriate candidates for inclusion in studies is an appropriate pre-entry activity. While a PI, Sub-Investigator or Study personnel may discuss availability of studies and the possibility of entry into the Study with a prospective participant without first obtaining consent, informed consent must be obtained prior to initiation of any clinical procedures that are performed solely for the purpose of determining eligibility for research.

Procedures that are to be performed as part of the practice of medicine and which would be done whether or not Study entry was contemplated, such as for diagnosis or treatment of a disease or medical condition, may be performed and the results subsequently used for determining Study eligibility without first obtaining consent. On the other hand, informed consent must be obtained prior to initiation of any clinical screening procedures that is performed solely for the purpose of determining eligibility for research. The PI, Sub-Investigator or Study personnel should take extra care to clarify with their patient-participants why certain tests are being conducted.

Any participant that screen-fails prior to or following their consent should be tracked. The *Screening & Enrollment Log* will be maintained by the Site and submitted to the Sponsor as changes occur.

### B. Enrollment

Participants who are eligible for inclusion in the Study will be asked to give his or her informed consent (*Template Informed Consent Document* is included as a supplemental document).KK This process will involve a discussion about the objectives of the Study, number of participants in the Study, follow up schedule and the procedure they will have including the surgical techniques and its foreseeable risks as well as potential benefits of participating in the Study.

The participant will be provided with the PIs contact details so that they can contact them with any questions. Participants will be informed that they are free to withdraw their consent at any time and this will not compromise any further medical care. In addition, the participant will be informed that the PI may terminate his/her participation without their consent.

The PI will also inform all participants that, should any unanticipated device related adverse effects occur during the Study which, in the opinion of the Sponsor, present unreasonable risks to the participants, all participants will be notified and participant enrollment will be terminated.

The participant will be informed by the PI that the Sponsor will verify that each participant has consented, in writing, to direct access to his/her original medical records for trial-related

KK Template informed consent document

monitoring, audit, IRB review, and regulatory inspection. Additionally, that his/her original medical records will be subject to review possibly by any legal authorities. This information will be used during the analysis of the results of the Study but the confidentiality of the participant will be maintained at all times.

A signed, written informed consent must be obtained from the participant by the PI (or designee) prior to the participant's involvement in the Study. Once a participant's consent has been obtained, a copy of the consent form will be provided to the participant. The original form will be maintained in the participant's research file. This consent is separate from the normal consent gained for any surgical procedures.

If the participant is a smoker, the Sponsor must be contacted prior to enrollment to ensure eligibility.

#### ***C. Unique Participant ID Assignment***

At the time of enrollment, a participant Study number will be issued which will be used on the CRFs, electronic records of data and any other Study documentation relating to that participant. The Study Site will assign the participant number in the following format: site # - participant # - participant initials (e.g., 03-01-ABC).

- The site's two digit number (assigned by the Sponsor).
- The PI (or designee) will assign the participant's two digit number in the order the participants are consented (e.g., sequentially 01, 02, etc.).
- The participant's first, middle and last name initials will be used. If there is no middle initial a “-“ may be used.

#### ***D. Pre-Operative Visit***

As a participant in the Study, information from the participant's medical record and pre-operative assessment will be recorded to verify eligibility (CRF 1). This information will include:

- Medical charts will be reviewed by the Study doctors. Participant's medical histories and clinical information from standard pre-operative diagnostic tools and routine tests, scans, and procedures to confirm the diagnosis and segments needing surgical intervention will be used for the Study (CRF 2).
  - History and Physical: e.g., start date of complaints, diagnosis and segments needing surgical intervention, pain level, previous non-operative treatments and current analgesia use, previous surgeries at the operative level, etc.
    - Information in a participant's medical chart from a recent visit to the PI or Sub-Investigator may be used to complete the form.
  - Clinical and Neurological Examination: e.g., Test reflexes, sensory deficits, muscle strength and physical limitations (CRF 3).

- Information in a participant's medical chart from a recent visit to the PI or Sub-Investigator may be used to complete the form.
- Diagnostic Tools and Routine Tests: e.g., questionnaires, plain x-rays, CT scan, MRI, DXA, discogram, bone density scan, bloods, ECG when necessary.
  - MRI should be within approximately 11 months of the surgery date or as routinely prescribed per the PI's pre-operative care.
- Routine plain x-rays will be taken, reviewed and transmitted (AP/LAT/FLX/EXT).
  - If all 4 x-rays were taken within the past 6 months, those x-rays may be transmitted to the independent radiologist.
- The participant will complete the following:
  - Women with the potential of being or becoming pregnant will confirm they are not pregnant.
  - Participant will complete self-administered questionnaires (CRF 4, CRF 5, CRF ODI and CRF 36-Item HS).

Completed CRFs should be faxed to the Sponsor following the visit. All completed plain radiographic films should be transmitted to MMI following the visit.

#### ***E. Surgery and Discharge Information***

Operative and discharge reports shall be submitted to the Sponsor with the completed CRFs (participant name, medical record number or account number must be redacted). As a participant in the Study, information from the surgery, hospital stay and discharge will be recorded by the PI (or designee).

- CRF 6: Participants will be evaluated pre- and intra-operatively and information about the surgery and hospital stay notes/events/procedures/x-rays will be used for the Study. This information will include:
  - Date of surgery
  - Operated segment(s)
  - Duration of surgery (time)
  - Procedures performed
  - Devices used
  - Amount of autograft used in and around the IBF device (as applicable)
  - Amount of autograft used in the posterolateral spine
  - Amount of BMA used to hydrate nanOss Bioactive 3D
  - Amount of nanOss Bioactive 3D used
  - Location of autograft and BMA harvesting
  - Estimated amount of blood loss (cc)
  - Complications or adverse events
- Participants will be evaluated at discharge (CRF 7 and CRF 8):
  - Information about discharge notes/events/procedures/x-rays will be used for the Study. This information will include:

- Date of discharge
- Medication prescribed at discharge
- Type of orthotics prescribed
- Type of facility where participant was discharged
- Complications or adverse events
- A clinical and neurological examination will take place prior to discharge. The doctor will test reflexes, sensory deficits, muscle strength and physical limitations.

Completed CRFs should be faxed to the Sponsor following the discharge date. A de-identified operative report should be included with the CRFs.

#### ***F. Post-Operative Regimen***

Post-operative patient management and care should follow the same regimen as routinely prescribed by the PI. The use of internal or external bone growth (or fusion) stimulators is not permitted on patients that participate in the Study.

#### ***G. Post-Operative Visits***

As part of routine post-operative care, participants are evaluated periodically by the surgeon. Information from the participant's post-operative visits will be collected. Postoperative visit windows are based off of the participant's date of surgery.

##### **1. 6 Months Postoperatively (6 months +/- 4 weeks):**

Medical charts will be reviewed by the Study doctors.

- The PI or designee will perform a routine post-operative clinical and neurological evaluation and complete CRF 8.
- Routine plain x-rays will be taken, reviewed and transmitted (AP/LAT/FLX/EXT).
- The PI will assess fusion status using Lenke's criteria and complete CRF 9.
- The PI or designee will review for any complications or adverse events since their discharge from the hospital.
- The participant will complete the self-administered questionnaires (CRF 10, CRF 11, CRF ODI and CRF 36-Item HS).

##### **2. 12 Months Postoperatively (12 months + 8 weeks):**

Medical charts will be reviewed by the Study doctors.

- The PI or designee will perform a routine post-operative clinical and neurological evaluation and complete CRF 8.
- A thin-slice ( $\leq$  1.25 mm) lumbar CT scan (without contrast) with coronal and sagittal mpr will be taken and transmitted.
- Routine plain x-rays will be taken, reviewed and transmitted (AP/LAT/FLX/EXT).
- The PI will assess fusion status using Lenke's criteria and complete CRF 9.

- The PI or designee will review for any complications or adverse events since the 6 month postoperative visit.
- The participant will complete the self-administered questionnaires (CRF 10, CRF 11, CRF ODI and CRF 36-Item HS).

### **3. 24 Months Postoperatively (24 months + 8 weeks):**

Medical charts will be reviewed by the Study doctors.

- The PI or designee will perform a routine post-operative clinical and neurological evaluation and complete CRF 8.
- If clinically indicated (including if no posterolateral bridging bone observed on the 12 month CT scan by the independent radiologist), a thin-slice ( $\leq 1.25$  mm) lumbar CT scan (without contrast) with coronal and sagittal mpr will be taken and transmitted.
  - If the participant is asymptomatic and does not want another CT scan, they may opt out of the 24 month CT scan while remaining in the Study.
  - If a thin-slice lumbar CT scan with sagittal and coronal mpr was taken within 6 months of the 24 month appointment for the entire treated area, that CT may be transmitted to the independent radiologist instead of another CT being completed.
- Routine plain x-rays will be taken, reviewed and transmitted (AP/LAT/FLX/EXT).
- The PI will assess fusion status using Lenke's criteria and complete CRF 9.
- The PI or designee will review for any complications or adverse events since the 12 month postoperative visit.
- The participant will complete the self-administered questionnaires (CRF 10, CRF 11, CRF ODI and CRF 36-Item HS).
- The PI or designee will complete CRF 12.

Completed CRFs should be faxed to the Sponsor following each visit. All completed plain radiographic films and the CT scan should be transmitted to MMI following each visit.

